#### 21.5 Safety Analysis

Safety variables to be analyzed are AEs, laboratory test results (hematology and clinical chemistry), ECG, weight, and vital signs.

Adverse event terms recorded on the eCRFs will be mapped to preferred terms using the Medical Dictionary for Drug Regulatory Activities (MedDRA®) version 10.1 or later. All AEs will be summarized according to the system organ class and preferred term within the organ class. Adverse events will be tallied for overall frequency (number and percentage of subjects), worst reported severity, and relationship to study drug for each preferred term per subject. Serious adverse events will be similarly summarized. Listings of deaths, SAEs, and AEs leading to early termination of study treatment or premature withdrawal from study will also be provided.

Laboratory variables will be examined using mean change in value from baseline to scheduled time points. Laboratory values will also be categorized according to their CTCAE (version 4) toxicity grade and tabulated by worst on-study toxicity grade. The baseline value of a variable is defined as the last value obtained on or before the date and time of the first PLX3397 dose.

ECG, weight, and vital signs will also be summarized by changes from baseline to scheduled time points using descriptive statistics.

## **21.6 Pharmacokinetic Analysis**

For the Phase 1b portion of the study, a partial AUC (AUC0-6) will be calculated using samples collected from C1D8 (pre-temozolomide) and C1D15 (concurrent temozolomide). Values for Cmax and Tmax will be determined from the concentration-time profile.

A formal PK statistical analysis plan will be created for this protocol, and a separate formal PK report will be written for inclusion in the final study report.

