Study Procedures	
After providing informed consent, patients will undergo screening for eligibility to participate in the study. Screening will start within 3 weeks prior to PLX3397 dosing. Following recovery from surgical resection, patients who meet inclusion/exclusion criteria will start study drug on the morning of any Monday through Friday (Cycle 1 Day 1; C1D1). This visit should occur between 3 weeks and 5 weeks after surgery. Patients will continue to dose study drug twice daily either 7 days/week or 5 days/week (Monday through Friday) and return to the clinic for evaluation on C1D8, the day they initiate radiation therapy plus temozolomide.
 
For the Phase 1b portion of the study, a blood sample will be obtained pre-dose on C1D1 for the baseline PK. On C1D8 and on C1D15, blood samples will be obtained pre-dose and 1, 2, 4, and 6 hours post-dose to estimate PLX3397 PK. Patients will return to the clinic on Cycle 2 Day 1 (C2D1) for evaluation. If PLX3397 has been well tolerated and there has been no clinical evidence of disease progression, continued dosing will be permitted. Patients will be monitored for response and disease progression with MRI brain scans every 2 cycles, with the brain scan obtained approximately 3-4 weeks after the completion of RT serving as the baseline scan for determination of progression.
 
For Phase 1b PLX3397 dose and schedule cohorts and escalation, see Study Design (above.)
 
For the Phase 2 portion of the study, patients will be treated with PLX3397 at the RP2D level.
 
For both phases, patients will be monitored throughout the study for adverse reactions to the study drug and/or study procedures.
 
Hematology assessments (i.e., CBC, differential count, and platelet count) will be performed weekly starting with C1D1 and continuing through the first week of the Recovery Period (RPD8). Serum chemistry assessments will be performed at Screening, C1D1, C1D15, C2D1, and C2D22 (completion of RT). For the adjuvant treatment period, assessments will be made on the day of treatment initiation (C3D1), C3D22, and D22 of each subsequent cycle, and at study completion or upon early withdrawal. A serum pregnancy test will be completed at Screening for applicable patients.
 
Blood pressure, respiratory rate, pulse rate and temperature will be measured at each study visit. A standard 12-lead electrocardiogram (ECG) will be performed for each patient at Screening, C1D1, C2D1, and study completion.
 
A complete physical examination will be performed for each patient at Screening. A neurological exam and a symptom-directed physical exam will be completed on each subsequent visit while continuing study therapy, and at study completion or upon early withdrawal. Patients will also complete the MD Anderson Symptom Inventory-Brain Tumor Module at the time points noted in the Trial Flow Chart, and Karnofsky performance status will be recorded as noted.
 
A surgical paraffin tumor block (or at least 20 unstained slides) will be identified during Screening for subsequent shipment to the central pathologist. Blood samples for circulating CSF-1, biomarkers of kinase inhibition and myeloid cell recruitment will be obtained pre-dose on C1D1, C1D8, C2D1, and C3D1. CD14/16 mononuclear cell counts will be obtained pre-dose on C1D1 and C1D8.
 
Commencing on 01 October 2017, patient visits, clinical laboratory testing, and MRI brain scans will be performed approximately every 12 weeks (please refer to the TRIAL FLOW CHART – Phase 2 for details).

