7. Blood samples for circulating CSF-1 and biomarkers of kinase inhibition and myeloid cell recruitment will be obtained pre-dose on C1D1, C1D8, C2D1, and C3D1. CD14/16 mononuclear cell counts will be obtained pre-dose on C1D1 and C1D8. Samples will be collected and processed by LabCorp according to the study-specific laboratory manual. LabCorp will perform the MGMT analyses.
8. For women of child-bearing potential. At screening, obtained within 14 days of the first dose of study drug.
9. A diagnostic contrast-enhanced MRI or CT scan of the brain must be performed preoperatively and postoperatively prior to the initiation of radiotherapy, i.e. within 28 days (14 days preferred) prior to study drug administration (C1D1). Patients unable to undergo MR imaging because of non-compatible devices can be enrolled, provided pre- and post-operative contrast-enhanced CT scans are obtained and are of sufficient quality.
10. Two PLX3397 BID administration schedules, 7 days/week vs. 5 days/week (M-F) will be explored for Cycle 1 and 2. PLX3397 will be administered BID 7 days/week for Cycle 3 and subsequent cycles until disease progression disease or unacceptable toxicity.
11. Temozolomide is taken orally once daily for 5 days followed by 23 days without treatment for each cycle beginning with C3D1 for up to 12 cycles.
12. Monitored throughout the study via safety assessments, observation, and participant reporting.
13. Standard 12-lead ECG with QTcF calculation. Fridericia's formula is required.  $QTcF = (QT)^3 \sqrt{(RR)}$

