### 7.5 Previous Human Experience

The ongoing Phase 1 dose escalation study PLX108-01 in patients with solid tumors is designed to evaluate the safety and PK of PLX3397. As of June 2012, a total of 62 patients have been treated with PLX3397, including 41 patients in the dose escalation cohorts and 21 patients in the Extension cohorts. The recommended Phase 2 dose has been established at 1000 mg/day. Plasma concentrations of PLX3397 demonstrate a  $T_{max}$  of approximately 2 hours, a mean elimination half-life of approximately 20 hours, and a mean accumulation ratio compared to Day 1 values of approximately 2-fold. In general, there is increasing exposure with increasing dose. Other single agent studies ongoing or completed include refractory Hodgkin lymphoma, Flt3-ITD+ AML, castrate-resistant prostate cancer, and recurrent GBM. Combination studies with paclitaxel and Eribulin are also ongoing.

In the recurrent GBM study, as of 13-Dec-2012, a total of 34 patients have been enrolled. Of these, 23 patients have discontinued study drug due to progressive disease (n = 21) or SAEs (n = 2). A total of 11 patients are ongoing, with 6 patients to be recruited. In general, the tolerability of study drug in this patient population has been similar to other patients with solid tumors, with few patients requiring drug holidays or dose reductions. Importantly, the concentration of PLX3397 measured in the tumor tissue of the 12 patients treated with 7 days of neoadjuvant therapy was similar to plasma concentrations, confirming the robust penetration of PLX3397 across the blood brain barrier in humans with GBM.

As of June 2012, a total of 107 patients have been treated to date. There have been no safety signals in vital signs, physical examinations, or ECGs (including careful evaluation of potential

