### 13.2 Cycle 1 Day 1 (- 2 Days), [4 week cycle]

The C1D1 visit must occur any Monday through Friday  $\geq 3$  weeks and  $\leq 5$  weeks since surgery. At this visit, all patients will return to the clinic and undergo the following procedures:

1. Weight, vital signs, neurological exam plus symptom-directed physical examination.

2. Clinical laboratory evaluation (hematology and serum chemistry).
3. For Phase 1b dose escalation patients only: Pre-dose blood sample collection for PK.
4. Pre-dose blood sample collection for PD response biomarkers and CD14/16 mononuclear cell counts.
5. Karnofsky performance status assessment.
6. MDA Symptom Inventory.
7. Recording of concomitant medications.
8. Initiation of dosing with study drug either 7 days/week or 5 days/week (Monday through Friday).
9. AE Monitoring, beginning after first dose of study drug.

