### **13.3 Cycle 1 Day 8 ( $\pm$ 2 Days), [4 week cycle]**

On C1D8, all patients will return to the clinic and undergo the following procedures:

1. Vital signs, neurological exam plus symptom-directed physical examination.
2. Clinical laboratory evaluation (hematology and serum chemistry).
3. For Phase 1b dose escalation patients only: Pre-dose and 1, 2, 4, and 6 hours post-dose blood sample collection for PK.
4. Pre-dose blood sample collection for PD response biomarkers and CD14/16 mononuclear cell counts.
5. Study drug compliance.
6. Recording of concomitant medications.
7. AE monitoring.
8. Initiation of radiation therapy and temozolomide.

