## **14.0 STUDY DRUG**

### **14.1 Study Drug Administration**

PLX3397 will be dosed orally using a capsule formulation (200 mg per capsule), twice daily in the fasting state with 240 mL (8 oz) of room-temperature water. The PLX3397 daily dose should be divided and administered twice daily approximately 12 hours apart. When the dose cannot be evenly divided, the higher of the two doses should be administered in the morning. For example, the PLX3397 1000 mg daily dose should be divided 600/400 AM/PM. For each dose, the patient should fast at least 1 hour before and 1 hour after administration. Patients will be permitted to eat a low-fat snack (e.g., crackers, toast, tea) during the fasting period if needed.

Temozolomide will be administered once daily, either in the morning or evening, also in the fasting, as noted in Section 16, either before or after PLX3397.

Study drug should be taken at approximately the same times of day, approximately 12 hours apart. On PK collection days, the morning dose of PLX3397 will be given at the clinical site; patients should be instructed NOT to take the study drug at home the morning of the clinic visit. The time of dosing will be recorded; patients will then take the evening dose at home. Between clinic visits, patients will take the study drug at home and record dosing information on the dosing diary. Missed doses (generally outside of a + 2 hour dosing window) should be skipped and not administered as a double dose at the next administration. Patients who vomit their dose should be instructed to NOT to make up that dose.

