## **16.0 TEMOZOLOMIDE THERAPY**

### **16.1 Temozolomide During Concomitant Radiation Therapy**

Temozolomide will be administered continuously from day 1 of radiotherapy to the last day of radiotherapy at a daily oral dose of  $75 \text{ mg/m}^2$  for a maximum of 49 days. The drug will be administered orally 1 hour before each session of radiotherapy during weekdays (Monday through Friday). During weekends without radiotherapy (Saturday and Sunday), the drug will be taken in the morning.

The dose will be determined using actual body surface area (BSA) as calculated in square meters at the beginning of the concomitant treatment. The BSA will be calculated from the height obtained at the pretreatment visit and the weight obtained at the visit immediately before the first day of treatment. Capsules of temozolomide are available in 5, 20, 100, 140, 180, and 250 mg. The daily dose will be rounded to the nearest 5 mg. If the investigator does not want to prescribe the temozolomide 5 mg unit strength, he/she should round off the dose to the closest 10 mg. For example, for a  $1.7 \text{ m}^2$  subject, the  $75 \text{ mg/m}^2$  dose would be 127.5 mg and the dose would be rounded off to 120 mg. For the same subject, the  $150 \text{ mg/m}^2$  dose would be 255 mg and the dose would be rounded off to 260 mg. The exact dose administered should be recorded in the CRF. Each daily dose should be given with the least number of capsules.

Patients will be instructed to swallow the capsules whole, in rapid succession, without chewing them. If vomiting occurs during the course of treatment, no re-dosing of the patient is allowed

before the next scheduled dose. The capsules should be taken on an empty stomach, therefore a minimum of 2 hours after eating and with no food consumption for at least 1 hour after temozolomide administration. Although, nightly administration just before bedtime has been reported to improve tolerance, the low daily dose administered during radiation is very well tolerated and administration in the morning before radiation dosing is required for this protocol. Administration of the higher dosing regimen during the adjuvant phase of the protocol should be performed using the nightly administration.

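### The C1D8 AUC0-6 called pre-temozolomide is drawn on the day temozolomide starts, and on the Monday–Friday schedule its size depends on the start weekday

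*Combined protocol and SAP*

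**What the plan says.** Section 21.6, and the PK entry of the synopsis, define two Phase 1b profiles: "samples collected from C1D8 (pre-temozolomide) and C1D15 (concurrent temozolomide"). Each has samples before the PLX3397 dose and 1, 2, 4 and 6 h after it.

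The rest of the protocol places the first profile on the first day of temozolomide:

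- The synopsis describes "C1D8, the day they initiate radiation therapy plus temozolomide". Section 13.3 lists "Initiation of radiation therapy and temozolomide" as the last item of that visit, with no clock time.
- Section 16.1 gives temozolomide 1 hour before radiotherapy on weekdays and adds that "administration in the morning before radiation dosing is required for this protocol".
- Section 14.1: "On PK collection days, the morning dose of PLX3397 will be given at the clinical site". The same section allows temozolomide in the morning or evening, before or after PLX3397, while referring to Section 16.

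On weekdays, Section 13.2 says "The C1D1 visit must occur any Monday through Friday". Three of the five Phase 1b cohorts (Table 2, footnote b: 600, 800 and 1000 mg/day) take PLX3397 Monday to Friday only during Cycles 1 and 2. C1D8 and C1D15 each have a ±2-day window. PD blood "will be obtained pre-dose on C1D1, C1D8, C2D1, and C3D1"; CD14/16 counts are taken pre-dose on C1D1 and C1D8 only.

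**The concern.** The two labels in Section 21.6 set up one contrast: PLX3397 exposure without and with temozolomide. That contrast needs a first profile free of temozolomide. If temozolomide is taken during the six hours of sampling, the profile is mislabelled, and a later PK analysis plan cannot recover a profile that was never drawn.

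The second issue is carry-over. PLX3397 has "a mean elimination half-life of approximately 20 hours" (Section 7.5), so its level on a given morning depends on the preceding dosing days. On the Monday–Friday schedule, C1D8 follows 0, 1, 2, 3 or 4 consecutive dosing days for a Monday, Tuesday, Wednesday, Thursday or Friday start. A reader setting 5-day against 7-day cohorts on C1D8 would mix schedule with start weekday. The same applies to the C1D8 CD14/16 count, the only one taken on treatment. PK is a secondary objective and PD exploratory, so the stake is how exposure and target inhibition are interpreted, not the primary endpoint.

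**Working it through.** The plan states no figure to reproduce, so I modelled what the timing rules imply if temozolomide has no effect on PLX3397.

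**Step 1: temozolomide inside the PLX3397 window.** Section 16.3.2 gives temozolomide a half-life of 1.8 h and a peak at about 1 h. With first-order absorption and elimination, the share of that dose's AUC falling before the 6 h PLX3397 sample is:

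| Temozolomide taken after PLX3397 dose | Share before 6 h |
|---|---|
| 0 h | 88% |
| 1 h | 82% |
| 2 h | 74% |
| 4 h | 43% |
| 6 h or later | 0% |

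**Step 2: weekend carry-over.** Inputs are half-life 20 h and Tmax 2 h (Section 7.5), with doses 12 h apart (Section 14.1). The one-compartment form is my assumption.

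- ke = ln 2/20 = 0.0347 per h. Solving ln(ka/ke)/(ka − ke) = 2 gives ka = 2.08 per h.
- Friday evening to Monday morning is about 60 h: 2^(−60/20) = 12.5% remains, against 2^(−12/20) = 66% after 12 h.
- Trough, 7-day schedule, 14 doses: 0.66/(1 − 0.66) × (1 − 0.66^14) ≈ 1.94.
- Trough, Monday start on 5 days, 10 doses: 0.125/(1 − 0.66) × (1 − 0.66^10) ≈ 0.36. Ratio 0.19.
- AUC0-6 by trapezoid at 0, 1, 2, 4, 6 h, equal doses: the new dose adds 4.85 and carry-over adds 1.017 × trough × 5.42, where 1.017 = ka/(ka − ke). The 7-day value is 4.85 + 10.66 = 15.5; the Monday-start value is 4.85 + 1.99 = 6.84. Ratio 0.44.

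Table 2 and Section 14.1 put the larger dose in the morning when capsules do not divide evenly, so I repeated this for each split. C1D8 AUC0-6, 5-day over 7-day at the same daily dose:

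| Start | 800 mg (400/400) | 600 mg (400/200) | 1000 mg (600/400) |
|---|---|---|---|
| Mon | 0.44 | 0.51 | 0.48 |
| Tue | 0.76 | 0.79 | 0.77 |
| Wed | 0.89 | 0.91 | 0.90 |
| Thu | 0.95 | 0.96 | 0.96 |
| Fri | 0.98 | 0.98 | 0.98 |

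The trough ratios are 0.19, 0.65, 0.85, 0.93 and 0.97 for every split. Weekly mean exposure would be 5/7 = 0.71, so a single C1D8 profile reflects start weekday as much as schedule. Only 600 and 800 mg/day have cohorts on both schedules.

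**Step 3: within-patient ratio with no interaction.** On nominal days C1D8 and C1D15 share a weekday, and C1D15/C1D8 is 1.00 for every start day and both schedules. If a Monday-start, 5-day patient has C1D8 on Monday and C1D15 two days late on Wednesday, the ratio is 2.03 (400/400), 1.79 (400/200) or 1.87 (600/400). With C1D8 on Wednesday and C1D15 on Monday it is 0.49 to 0.56.

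**Step 4: sensitivity.** Over half-lives of 15 to 25 h (an assumed range), the Monday ratio is 0.44 to 0.46 with equal doses and 0.50 to 0.54 with 400/200. At 20 h with equal doses the model implies 3.2-fold accumulation of AUC0-6 from day 1 to day 8. Section 7.5 reports about 2-fold without giving the dosing interval, so the model may overstate carry-over. At 15 h with 400/200, accumulation is 2.06 and the Monday ratio is still 0.54.

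**Step 5: a run-in sampling day.** On the last weekday before C1D8 (Day 5 for a Monday start, otherwise Day 7), repeated 7 days later, the no-effect ratio at 20 h is 1.00 to 1.03. An early run-in day is worse: Day 3 for a Wednesday start on the 5-day schedule gives 1.11 to 1.13.

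**The case against.** Several points on the other side have force.

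- Section 14.1 permits evening temozolomide. On that reading the whole C1D8 profile is clean, so one cannot say it is never pre-temozolomide. This stands, but it rests on text at odds with Section 16.1. The order of items in Section 13.3 does not settle it, since that list carries no times.
- A reader might infer that the C1D8 PD samples are mislabelled too. The documents do not support that: the label covers only the PK AUC, and the PD samples and the first PK sample are pre-dose. They precede temozolomide unless it is taken before PLX3397.
- A reader might infer that the weekend gap makes a temozolomide effect undetectable. It does not: on nominal days it cancels within patient, and the 7-day cohorts have no gap. The artefact needs a 5-day cohort, an early-week visit and uneven use of the windows.
- A reader might infer that the two schedules cannot be compared. No PK comparison of schedules is pre-specified. Schedules are judged on DLTs, PD is descriptive (Section 21.7.2), and a separate PK analysis plan is promised. That plan could handle weekday: Sections 14.1 and 20.1 already record the PLX3397 dose time on PK days, a dosing diary and actual sample times. It could not recover a temozolomide-free profile.
- Section 7.3 does not anticipate relevant drug interactions on CYP grounds, and Section 16.3.3 gives CYP enzymes a minor role for temozolomide. The true effect may be small. That lowers the stakes but does not make the label correct.

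**Conclusion.** The point holds in two parts of different weight.

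First, the pre-temozolomide label on the C1D8 AUC0-6 is not secured, and under the morning rule of Section 16.1 it will normally be wrong. This follows from the documents; only the size of the overlap, 43% to 88% of the temozolomide dose's AUC for dosing 0 to 4 h after PLX3397, rests on a model.

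Second, C1D8 PK on the Monday–Friday schedule varies about two-fold with start weekday: 0.44 to 0.51 of the 7-day value for a Monday start, 0.98 for a Friday start. The planned within-patient contrast survives this if the weekday match is kept; if it is broken, a 1.8- to 2.0-fold change can appear with no interaction. A between-schedule reading of C1D8 PK or CD14/16 is confounded by start weekday unless this is accounted for. These sizes assume linear one-compartment kinetics, a 20 h half-life and full adherence. The Monday-start deficit persists across the sensitivity range.

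Even a clean pair of profiles differs by the start of RT as well as temozolomide, so a change could not be assigned to temozolomide alone. The matter should be corrected, but it touches secondary and exploratory endpoints only.

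**What to change.** Sampling and reporting change; dosing does not.

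1. Reconcile Sections 14.1 and 16.1 on the timing of temozolomide during RT.
2. Take the Phase 1b pre-temozolomide profile on a run-in weekday before the first temozolomide dose, as late in the run-in as practicable. Step 5 suggests the last weekday before C1D8.
3. Take the concurrent profile on the same weekday after temozolomide has started, and do not let the visit windows break that match.
4. Record the temozolomide clock time on PK days, alongside the PLX3397 and sampling times already captured.
5. In the PK analysis plan, name the contrast. State that any change also coincides with RT and, for early run-in samples, with residual accumulation.
6. When comparing 5-day and 7-day cohorts, report C1D8 PK and PD by number of consecutive dosing days and time since last dose.

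If Phase 1b sampling is already complete, relabel the C1D8 AUC0-6 as first day of temozolomide wherever temozolomide was taken before the 6 h sample, and apply item 6 from the recorded times.

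The cost is an amendment to the Phase 1b flow chart and Sections 13.3, 13.4 and 21.6, and one extra attendance in the run-in week for some Phase 1b patients. The number of PK samples is unchanged, and the second profile falls on a weekday, when RT is scheduled.
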